5.4. Suspected ARI Visit

Subjects requiring Suspected ARI Visit will be evaluated as follows:

1. Physical examination as warranted by the Investigator for any change from baseline.
2. Body weight and collection of vital signs to include blood pressure, pulse, respiratory rate and body temperature.

3. Collect a nasopharyngeal swab sample using a single nylon flocculated dry swab inserted into both nostrils for RT-PCR at the Suspected ARI Visit, 24 to 36 hours later, and then again 4 to 5 days later.
4. Collect a fecal specimen for RT-PCR at the Suspected ARI Visit, 24 to 36 hours later, and then again 4 to 5 days later.
5. The subject will complete a FLU-PRO[®] symptom diary daily until he/she responds “yes” to the FLU-PRO[®] question, “Have you returned to your usual health?” for 3 consecutive days or until the Week 8 Visit, whichever occurs first. The daily FLU-PRO[®] diary will be completed between 7:00 pm and 11:00 pm.
6. Review and recording of concomitant medications.
7. Review and recording of adverse events/side effects.
8. Laboratory investigations for safety may be performed as warranted based upon the Investigator’s judgment.
9. If a subject tests positive for a respiratory virus by RT-PCR, that subject may receive standard of care as clinically warranted by the Investigator.

Regardless of symptoms or laboratory data, the subject will continue treatment until the 6-week treatment period has ended.

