10. ADVERSE EVENTS

The term “adverse event” is defined for purposes of this study as any unwanted physical, psychological or behavioral change experienced by a subject during the course of the study and after taking the first dose of study medication regardless of its severity or relation to the study. Adverse events may include symptoms, signs, unexpected worsening of pre-existing conditions, clinically significant changes in laboratory values, diseases and syndromes, and significant and unexpected failures of pharmacological action of other medications. Symptoms of VRIs (cough, sore throat, nasal obstruction, fatigue, headache, myalgia, feverishness) and complications of VRIs will not be reported as adverse events.

Adverse events will be recorded on the appropriate EDC forms throughout the study, and the severity of each adverse event will be graded on a four-point scale: mild, moderate, severe, or life-threatening (See [Appendix II](#)). The duration of the adverse event and relationship to the study drug will also be recorded. All adverse events must be followed until their resolution or stabilization even beyond the planned study period.

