10.1. Definitions

The following definitions will apply to the reporting of adverse events:

1. Serious Adverse Event: Any adverse experience occurring at any dose that is fatal or life threatening; requires in-patient hospitalization or prolongation of an existing hospitalization; is a persistent significant disability/incapacity; is a congenital anomaly or birth defect; or is an important medical event that may not result in death, be life-threatening, or require hospitalization but, based upon appropriate medical judgment, may jeopardize the subject and may require medical or surgical intervention to prevent one of the outcomes listed above.
2. Unexpected Adverse Event: Any adverse experience that is not identified in nature, severity, or frequency in the Investigator's Brochure for NTZ.
3. Severity of adverse events will be assessed by the Investigator using the Toxicity Grading Scale Tables provided in [Appendix II](#) (derived and adapted from "Guidance for Industry: Toxicity Grading Scale for Healthy Adult and Adolescent Volunteers Enrolled in Preventive Vaccine Clinical Trials", US Dept. of HHS, FDA, CDER, September 2007 and the National Institutes of Health, National Cancer Institute Common Terminology Criteria for Adverse Events (CTCAE) version 5.0).
4. Causality (relationship to treatment) will be assessed as follows:
 - *Definitely Related*: The adverse event is clearly related to the investigational agent(s) or research intervention: the adverse event has a temporal relationship to the administration of the investigational agent(s) or research intervention, follows a known pattern of response, and no alternative cause is present.
 - *Probably Related*: The adverse event is likely related to the investigational agent(s) or intervention: the adverse event has a temporal relationship to the administration of the investigational agent(s) or research intervention, follows a known or suspected pattern of response, but an alternative cause may be present.
 - *Possibly Related*: There is a reasonable possibility that the event may have been caused by or is linked in a significant way to the research; the adverse event has a temporal relationship to the administration of the investigational agent(s) or research intervention, follows a suspected pattern of response, but an alternative cause is present.

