10.2. Clinical Adverse Events

At the time of each return visit, the subject will be questioned regarding the occurrence and nature of any adverse events. All events must be recorded in the subjects' medical records and in the EDC system. Any subject affected will be examined by the Investigator as deemed necessary to ascertain the course of the event and any residual effects.

All moderate and severe adverse events will be reviewed by the Principal Investigator who will determine using his/her best clinical judgment whether they warrant the subject to be discontinued from the study. The Sponsor will be notified immediately if a subject is discontinued from the study. For all adverse events that require the subject to be discontinued from the study, relevant clinical assessments and laboratory tests will be repeated as clinically indicated until final resolution or stabilization of the event(s).

All subjects will be instructed to contact the Investigator, Investigator's assistants, or clinical personnel should the subject have any serious adverse experiences. Serious adverse events, including death regardless of the cause, must be reported to the Sponsor immediately (within 24 hours of the initial report).

A serious event requiring immediate notification by telephone is an event that:

- results in death
- is life threatening
- requires inpatient hospitalization or prolongation of an existing hospitalization
- is a persistent or significant disability/incapacity
- is a congenital anomaly/birth defect
- an important medical event that may not result in death, be life-threatening, or require hospitalization but, based upon appropriate medical judgment, may jeopardize the subject and may require medical or surgical intervention to prevent one of the outcomes listed above.

An overdose is defined as any intentional or unintentional consumption of the drug by any route that exceeds the highest dose stated in the Investigator's Brochure or in an investigational protocol, whichever dose is larger. Overdoses without an associated adverse event should be recorded, but not reported as an adverse event.

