2.2 Analysis Populations

2.2.1 Population Definitions

Subjects will be considered enrolled in the study upon completion of the baseline procedures. The following analysis populations will be used in the study.

- **Safety Population** – the safety population includes all patients who are enrolled in the study and that have received at least one dose of the assigned treatment arm (NTZ or placebo).
- **Intention-to-Treat Population (ITT)** – the ITT population includes all patients in the safety population who did not have a laboratory detected respiratory virus infection at the baseline visit.

The safety population will be used for all safety analyses. The ITT population will be the primary population for all efficacy analyses.

A data listing displaying the patients excluded from the ITT population will be created, as shown in the Table Requirements Document. This listing will be relative to all patients in the safety population.

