14.2.3.2	Pearson Chi-square Test Results by Stratum: COVID-19 Antibody Test Status (ITT Population)
14.2.3.3	Cochran-Mantel-Haenszel Test Results: VRI Related Hospitalization Status (ITT Population)
14.2.3.4	Pearson Chi-square Test Results by Stratum: VRI Related Hospitalization Status (ITT Population)
14.2.3.5	Cochran-Mantel-Haenszel Test Results: VRI Related Mortality Status (ITT Population)
14.2.3.6	Pearson Chi-square Test Results by Stratum: VRI Related Mortality Status (ITT Population)
14.2.3.7	Cochran-Mantel-Haenszel Test Results: ARI Incidence Status (ITT Population)
14.2.3.8	Pearson Chi-square Test Results by Stratum: ARI Incidence Status (ITT Population)
14.2.3.9	Cochran-Mantel-Haenszel Test Results: ARI Related Hospitalization Status (ITT Population)
14.2.3.10	Pearson Chi-square Test Results by Stratum: ARI Related Hospitalization Status (ITT Population)
14.2.3.11	Cochran-Mantel-Haenszel Test Results: ARI Related Mortality Status (ITT Population)
14.2.3.12	Pearson Chi-square Test Results by Stratum: ARI Related Mortality Status (ITT Population)
14.3.1.1	Treatment Emergent Adverse Events Summary: Total AE, Toxicity Grade, Relationship to Treatment, Serious AEs by Treatment (Safety Population)
14.3.1.2	Treatment Emergent Adverse Events by System Organ Class, Preferred Term, and Treatment (Safety Population)
14.3.1.3	Treatment Emergent Adverse Events by System Organ Class, Preferred Term, Treatment, and Toxicity Grade (Safety Population)
14.3.1.4	Treatment Emergent Adverse Events by System Organ Class, Preferred Term, Treatment, and Relationship to Treatment (Safety Population)
14.3.1.5	Treatment Emergent Serious Adverse Events by System Organ Class, Preferred Term, and Treatment (Safety Population)
14.3.2.1	Clinical Laboratory Summary Statistics: Hematology (Safety Population)

Table No.	Table Title
14.3.2.2	Clinical Laboratory Shift Tables: Hematology (Safety Population)
14.3.3.1	Clinical Laboratory Summary Statistics: Clinical Chemistry (Safety Population)
14.3.3.2	Clinical Laboratory Shift Tables: Clinical Chemistry (Safety Population)
14.3.4.1	Clinical Laboratory Summary Statistics: Urinalysis (Safety Population)
14.3.4.2	Clinical Laboratory Shift Tables: Urinalysis (Safety Population)
14.3.5.1	Vital Signs Summary Statistics (Safety Population)

Listing No.	Data Listing Title
16.2.1	Subject Disposition Listing (All records)
16.2.2	Protocol Deviations Listing (Safety Population)

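### Two reporting rules conflict for a VRI hospitalisation, and under one of them an admission of a subject virus-positive at baseline can miss every summary table

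*Protocol*

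**What the plan says.** **Reporting rules.** Protocol Section 10 exempts the symptoms of VRIs from adverse-event reporting and adds that "complications of VRIs will not be reported as adverse events". It gives no exception for complications that meet a seriousness criterion. Section 10.1 counts as serious any adverse experience that "requires in-patient hospitalization or prolongation of an existing hospitalization". Section 10.2 states: "Serious adverse events, including death regardless of the cause, must be reported to the Sponsor immediately". Its list of events needing immediate telephone notification includes one that "requires inpatient hospitalization or prolongation of an existing hospitalization". Neither section carves out VRIs, and the SAP neither repeats nor resolves the exemption.

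**Populations.** SAP Section 2.2.1 limits the ITT population to Safety Population subjects "who did not have a laboratory detected respiratory virus infection at the baseline visit". Protocol Section 8.4.1 makes the same exclusion. The excluded subjects are still treated: Protocol Section 5.2 places the swab, randomisation and first dose at the baseline visit, and no step waits for the swab result. For a later Suspected ARI Visit, Section 5.4 adds: "Regardless of symptoms or laboratory data, the subject will continue treatment until the 6-week treatment period has ended".

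**Outputs.** In SAP Section 8.0, the VRI hospitalisation tables (14.2.3.3, 14.2.3.4) and ARI hospitalisation tables (14.2.3.9, 14.2.3.10) are all in the ITT population. The adverse-event tables (14.3.1.1 to 14.3.1.5) are in the Safety Population. Listing 16.2.6.2 gives hospitalisation status by subject in the Safety Population. SAP Section 6.3 calls for all-cause deaths by arm in the Safety Population.

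**The concern.** A COVID-19 pneumonia admission is a VRI complication, which Section 10 removes from adverse-event reporting. It is also a hospitalisation, which Sections 10.1 and 10.2 make serious and reportable. Two sites could handle the same admission differently and each cite the protocol.

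One would normally rely on the efficacy tables to count the exempted events. That works for subjects who were virus-negative at baseline. It does not work for those who were positive, because the efficacy tables exclude them. The design makes such subjects likely: Protocol Section 4.1 requires healthcare workers to have had a known COVID-19 exposure in the 7 days before enrolment.

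At stake is a safety question: does nitazoxanide (NTZ) worsen an infection already present at the first dose? Non-fatal admissions are natural evidence on this, and the plan does not guarantee a by-arm summary of them.

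**Working it through.** No figure in the plan underlies this point, so the check is a trace. Take a dosed subject who was virus-positive at baseline and is later admitted, without dying, for a VRI complication.

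| Output | If the site applies the Section 10 exemption | If the site applies 10.1 and 10.2 |
|---|---|---|
| Tables 14.2.3.3, 14.2.3.4 (VRI hospitalisation) | Absent: ITT only | Absent: ITT only |
| Tables 14.2.3.9, 14.2.3.10 (ARI hospitalisation) | Absent: ITT only | Absent: ITT only |
| Tables 14.3.1.1 to 14.3.1.5 (adverse events) | Absent: SAP Section 5.2 builds them from adverse events | Present, including serious-event Table 14.3.1.5 |
| SAP Section 6.3 (deaths) | Absent: non-fatal | Absent: non-fatal |
| Listing 16.2.6.2 | Present, by subject | Present, by subject |

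Summary outputs reached: none under the exemption; the adverse-event tables under 10.1 and 10.2. The gap is therefore conditional on how the site reads the protocol.

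Three neighbouring cases are already summarised:

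- Deaths from any cause, through SAP Section 6.3.
- Non-VRI hospitalisations of baseline-positive subjects, who are in the Safety Population and so enter Table 14.3.1.5.
- VRI hospitalisations of baseline-negative subjects, through the ITT tables.

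**Size of the group.** Inputs: the expected sample of 2,842 and the approximately 4,000 needed for 90% power (Protocol Section 8.1; the Synopsis also caps enrolment at 4,000). Baseline positivity is not given; 1% to 10% is assumed.

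- Low: 0.01 × 2,842 = 28.4, about 28 subjects.
- High: 0.10 × 4,000 = 400 subjects.
- With 1:1 allocation, about half are on NTZ: roughly 14 to 200.

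**Number of admissions.** The documents give no hospitalisation rate. For illustration only, assume that 1% to 2% of this group is admitted with a VRI.

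- Low: 0.01 × 28.4 = 0.28.
- High: 0.02 × 400 = 8.

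That is somewhere between none and about eight admissions over both arms.

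**The case against.** The strongest case against is that the gap is narrow and partly guarded.

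- **The gap is conditional.** A reader might infer that VRI admissions of baseline-positive subjects always miss the summary tables. The documents do not support that, because a site following 10.1 and 10.2 puts them in Table 14.3.1.5. This stands.
- **The subjects are not lost.** A reader might also infer that baseline-positive subjects fall outside all hospitalisation reporting. They do not: their non-VRI admissions and deaths are summarised. This stands.
- **Appendix II does not contradict the exemption.** It grades headache, fatigue and myalgia, which Section 10 names as VRI symptoms. Section 10 exempts them only as VRI symptoms; the same complaints from other causes remain adverse events and need grades. There is no conflict here.
- **Section 10 also counts unexpected worsening of pre-existing conditions as an adverse event.** An infection present at the first dose might be read that way. The reading is possible, but the VRI exemption is the more specific sentence in the same paragraph and is not made subject to it. The ambiguity remains.
- **Other safeguards exist.** Protocol Section 10.3 requires immediate notice of fatal, life-threatening and unexpected experiences, and an IDMC monitors safety. Its charter is not among the documents. Neither safeguard provides a planned by-arm summary.
- **Site differences are noise, not bias.** Treatment is blinded and randomised, so nothing suggests that a site's reporting habit would depend on arm. This stands, and the safety analysis is descriptive.
- **A listing can display a handful of events.** True, but a listing is not a comparison by arm with denominators.

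**Conclusion.** The point holds in a limited form. The protocol does not say whether the VRI exemption covers events that meet a seriousness criterion. Where a site reads it as doing so, non-fatal VRI hospitalisations of baseline-positive subjects appear only in listing 16.2.6.2. Where a site reads it otherwise, they enter Table 14.3.1.5. Serious-event counts can therefore differ by site for the same kind of event.

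The group is about 28 to 400 dosed subjects, resting on the assumed 1-10% positivity. Admissions would be few. Neither the primary analysis nor any other ITT comparison is affected. What suffers is the completeness of the safety summary in a group where harm from treatment is plausible.

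**What to change.** 1. Reconcile Protocol Section 10 with Sections 10.1 and 10.2, so that it is explicit whether the VRI exemption covers events that meet a seriousness criterion. This costs one sentence.
2. Add to SAP Sections 5.2 and 6.3 one Safety Population table of hospitalisations, any cause and VRI-related, by arm and split by baseline virus status. It would sit beside the all-cause death summary. The inputs are already planned: hospitalisation status for listing 16.2.6.2, its cause as an efficacy variable in SAP Section 4.1, and the baseline swab result.

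The SAP approval is dated 26 April 2024, and Protocol Section 3 expected the study to run through April 2021. If conduct is complete, the sentence can no longer change site reporting and the table is the actionable part. The small downside is that some efficacy events will also appear in a safety summary; a footnote can say so.

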10.1. Definitions

The following definitions will apply to the reporting of adverse events:

1. Serious Adverse Event: Any adverse experience occurring at any dose that is fatal or life threatening; requires in-patient hospitalization or prolongation of an existing hospitalization; is a persistent significant disability/incapacity; is a congenital anomaly or birth defect; or is an important medical event that may not result in death, be life-threatening, or require hospitalization but, based upon appropriate medical judgment, may jeopardize the subject and may require medical or surgical intervention to prevent one of the outcomes listed above.
2. Unexpected Adverse Event: Any adverse experience that is not identified in nature, severity, or frequency in the Investigator's Brochure for NTZ.
3. Severity of adverse events will be assessed by the Investigator using the Toxicity Grading Scale Tables provided in [Appendix II](#) (derived and adapted from "Guidance for Industry: Toxicity Grading Scale for Healthy Adult and Adolescent Volunteers Enrolled in Preventive Vaccine Clinical Trials", US Dept. of HHS, FDA, CDER, September 2007 and the National Institutes of Health, National Cancer Institute Common Terminology Criteria for Adverse Events (CTCAE) version 5.0).
4. Causality (relationship to treatment) will be assessed as follows:
 - *Definitely Related*: The adverse event is clearly related to the investigational agent(s) or research intervention: the adverse event has a temporal relationship to the administration of the investigational agent(s) or research intervention, follows a known pattern of response, and no alternative cause is present.
 - *Probably Related*: The adverse event is likely related to the investigational agent(s) or intervention: the adverse event has a temporal relationship to the administration of the investigational agent(s) or research intervention, follows a known or suspected pattern of response, but an alternative cause may be present.
 - *Possibly Related*: There is a reasonable possibility that the event may have been caused by or is linked in a significant way to the research; the adverse event has a temporal relationship to the administration of the investigational agent(s) or research intervention, follows a suspected pattern of response, but an alternative cause is present.
 - *Unrelated (or Not Related)*: The adverse event is clearly NOT related to the investigational agent(s) or intervention: the adverse event has no temporal relationship to the administration of the investigational agent(s) or research intervention, follows no known or suspected pattern of response, and an alternative cause is present.

Under double-blind treatment conditions, it should be assumed that all subjects are taking the test drug.

10.2. Clinical Adverse Events

At the time of each return visit, the subject will be questioned regarding the occurrence and nature of any adverse events. All events must be recorded in the subjects' medical records and in the EDC system. Any subject affected will be examined by the Investigator as deemed necessary to ascertain the course of the event and any residual effects.

All moderate and severe adverse events will be reviewed by the Principal Investigator who will determine using his/her best clinical judgment whether they warrant the subject to be discontinued from the study. The Sponsor will be notified immediately if a subject is discontinued from the study. For all adverse events that require the subject to be discontinued from the study, relevant clinical assessments and laboratory tests will be repeated as clinically indicated until final resolution or stabilization of the event(s).

All subjects will be instructed to contact the Investigator, Investigator's assistants, or clinical personnel should the subject have any serious adverse experiences. Serious adverse events, including death regardless of the cause, must be reported to the Sponsor immediately (within 24 hours of the initial report).

A serious event requiring immediate notification by telephone is an event that:

- results in death
- is life threatening
- requires inpatient hospitalization or prolongation of an existing hospitalization
- is a persistent or significant disability/incapacity
- is a congenital anomaly/birth defect
- an important medical event that may not result in death, be life-threatening, or require hospitalization but, based upon appropriate medical judgment, may jeopardize the subject and may require medical or surgical intervention to prevent one of the outcomes listed above.

An overdose is defined as any intentional or unintentional consumption of the drug by any route that exceeds the highest dose stated in the Investigator's Brochure or in an investigational protocol, whichever dose is larger. Overdoses without an associated adverse event should be recorded, but not reported as an adverse event.

10.3. Reporting Requirement

The Principal Investigator is required to notify The Romark Institute for Medical Research (Sponsor) immediately of any unexpected, fatal, or life-threatening experience and all unusual, alarming, or serious reactions to medication regardless of any opinions as to the cause/effect relationship. All serious adverse events will also be reported to the IRB. Adverse events should be reported to:

The Romark Institute for Medical Research
Medical Affairs

██
██
██
██

